7.3 STUDY CENTERS

This study will be conducted at up to 15 centers in the United States. No center will have more than 20% of the target enrollment.

8 STUDY SELECTION CRITERIA

8.1 INCLUSION CRITERIA

[figure not shown]
For inclusion in this study, subjects must meet all of the following criteria:

- 1. At least 22 years of age
- Reports dry eye symptoms
- 3. Reports having to use artificial tears or lubricants regularly
- 4. OSDI Score
- 5. TBUT
- 6. Meibomian gland obstruction in both eyes
- 7. Best corrected visual acuity of 20/100 or better in both eyes.
- 8. Willing and able to comply with the study procedures and follow-up
- 9. Willing and able to provide informed consent

10. English-speaking

8.2 EXCLUSION CRITERIA

A subject who meets any of the criteria listed below (in either eye) will be excluded from the study:

3. History of eyelid, conjunctiva or corneal surgery (including refractive surgery) within the past year. In addition, subjects with any history of the following are excluded: chalazion surgery, surgery on the tarsal conjunctiva, radial keratotomy (RK), complicated blepharoplasty, lid reconstruction, or significant complications post-refractive surgery.

- 5. Meibomian gland expression within 6 months prior to enrollment.
- 6. In the clinical judgement of the investigator, meibomian glands have significant capping, atrophy, or are unable to be digitally expressed.
- 7. Contact lens use within the past 2 weeks. (
- 8.
- 9. History of Ocular Herpes Simplex or Ocular Herpes Zoster
- 10. Clinically significant ocular surface abnormalities that may affect tear film distribution or treatment (e.g. pterygium, anterior membrane dystrophy, etc.)
- 11. Clinically significant eyelid abnormalities in either eye (e.g. entropion/ectropion, blepharospasm, aponeurotic ptosis, lagophthalmos, notching of lid margin, distichiasis, trichiasis).
- 12. Clinically significant anterior blepharitis. In addition, collarettes or flakes of more than one quarter of the eyelid are excluded.
- Clinically significant dermatologic or cutaneous disease of the eyelid or periocular area.
- 14. Ocular trauma
- 15. Any active, clinically significant allergic, vernal, or giant papillary conjunctivitis.
- 16. Known history of diminished or abnormal facial, periocular, ocular or corneal sensation
- 17. Corneal surface abnormalities such as corneal epithelial defects (other than punctate staining), ulcers, corneal epithelial dystrophies, keratoconus, and

ectatic disease of the cornea

- 18. Punctal occlusion or punctal plug placement
- 19. Systemic diseases resulting in dry eye (e.g. autoimmune diseases such as Sjogren's syndrome, rheumatoid arthritis, lupus, Graves' disease, sarcoidosis, etc.)
- 20. Allergies to silicone tissue adhesives

21.

- 22. Use of antihistamines (oral or topical) within 10 days prior to enrollment.
- 23. Subject is currently on a systemic medication(s) (other than anti-histamines) that is known to cause ocular dryness⁴⁶ and whose dose of this medication(s) has not been stable within 30 days prior to enrollment.
- 24. Subject has taken or is currently taking Accutane.
- 25. Subject requires chronic use (i.e. for any portion of the study) of topical ophthalmic antibiotics, anti-glaucoma medications, steroids, non-steroidal anti-inflammatory medications
- 26. Subject is currently using Retin A or Latisse.
- 27. Participation in another ophthalmic clinical trial within 30 days prior to enrollment. Subject must also be willing to refrain from another ophthalmic study for the duration of the study.
- 28. Co-existing conditions that could interfere with the assessment of safety or effectiveness of treatment (e.g. macular disease, pregnancy, nursing, etc.).

9 STUDY PROCEDURES

9.1 STUDY SCHEDULE

The Study Schedule is shown below in Table 3.

9.2 NUMBER OF SUBJECTS, DURATION OF FOLLOW-UP AND STUDY DURATION

A total of 200 subjects will be enrolled and randomized in the study. Assuming a 15% screen failure rate, approximately 230 subjects will be enrolled and screened to obtain 200 randomized subjects. All subjects will be followed for 12 months.

It is anticipated that enrollment in the study will take 3-6 months. Including the 12-month follow-up period, the study is expected to last 15-18 months.

Analysis of the primary outcome will occur when the last subject has reached the 1 month follow up. In order to evaluate long-term results of the TearCare treatment, data will be re-analyzed after the last subject reaches the 6 month follow-up and then again after the last subject reaches the 12 month follow up.

9.4 INFORMED CONSENT AND POINT OF ENROLLMENT

The IRB-approved informed consent will be presented and explained to each prospective subject by the investigator or a trained clinical professional. Once the subject has had ample time to read the consent form, has been informed of all aspects of the study, and has had an opportunity to ask questions, the subject will be given a choice to voluntarily confirm his or her participation in the study as documented by completion of the Informed Consent. After signing the Informed Consent and the HIPAA (Health Insurance Portability and Accountability Act) authorization, the subject can then proceed with the baseline visit. The subject has the right to withdraw from the study at any time without consequences, as indicated in the Informed Consent Document.

The subject's signed and dated informed consent must be obtained before conducting any procedure specifically for the study. Subjects are enrolled upon signing the ICD even if they subsequently fail to meet the eligibility criteria.

The principal investigator(s) must retain the original, signed written Informed Consent Document. A copy of the written Informed Consent Document must be given to the subject.

9.5 BASELINE VISIT

9.5.1 SCHEDULING THE BASELINE VISIT

The baseline visit may be performed over two separate visits. If the visit is performed over two visits, then all baseline exams and questionnaires (Section 9.5.2) and randomization (Section 9.5.3) should be performed in the first visit. If the subject is randomized to the warm compress and lid massage group, the treatment for warm compress and lid massage (Section 9.5.5), and the associated discomfort/pain questionnaire and AE assessment should be performed at the first visit. If the subject is randomized to TearCare, then the TearCare procedure (Section 9.5.4) and the associated Discomfort/pain questionnaire and AE assessment may be performed on a separate visit, as long as it is performed within 7 days of the first visit. If the TearCare procedure is performed on a second visit, then the date of the second visit will be Day 0 of the study for scheduling purposes.

Endpoint assessments performed during the Baseline visit must be performed by the Masked Assessor (See Section 9.7).

Since dry eye drops and lubricants can affect the endpoint assessments, instruct subjects not to use any of these products within 2 hours of the Baseline visit.

[figure not shown]
9.5.3 RANDOMIZATION

Subjects will be randomized to either the TearCare (i.e. "treatment group") or Warm Compress and Lid Massage (i.e. "control group") using a pseudo-random number generator with subjects enrolled according to a predetermined list. Randomization will

use permuted blocks with random block sizes of 2 or 4. The investigational site will be provided a set of envelopes with randomization assignments. Following randomization, the subject should immediately undergo the applicable procedures described in the sections below.

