7 STUDY DESIGN

This is a prospective, randomized, controlled, single-masked, multi-center treatment study. This is a post-market study intended to collect data to update the indication for use for the TearCare System. To reduce potential bias in the study, study staff performing the endpoint assessments will be masked as to the subject's treatment arm. Subjects cannot be masked as it will be obvious to them which treatment they are receiving.

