9.7 MASKED ASSESSOR

To reduce potential bias in the study, study staff performing endpoint assessments will be masked as to the subject's treatment arm. In addition, to ensure consistency in performing the endpoint assessments the study staff member who performs the baseline assessments should also perform the follow-up assessments. An alternate Masked Assessor may be appointed to handle scheduling conflicts, but every effort should be made to have the same person performing all endpoint assessments throughout the study. The Masked Assessor should not perform the randomization, inoffice TearCare Treatment, gland expression or the in-office warm compress treatment prior to home use. Masking will be maintained until all subjects at the site have passed the 6-month follow up time.

The following assessments must be performed by Masked Assessor:

- Manifest refraction and BCVA
- Slit lamp exam
- Tear Break-up Time
- Corneal and conjunctival staining
- Meibomian gland secretion scoring
- IOP
- AE assessment

The study coordinator should collect the Warm Compress Log from the subject.

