12.7 SAMPLE SIZE CALCULATION

A total of 200 subjects, 100 in the TearCare group and 100 in the Warm Compress group, will be enrolled and randomized in the study. Sample size was calculated to provide more than 90% power for the TBUT and OSDI effectiveness endpoints and sufficient precision around the adverse event estimates. The sample size also takes into account an estimated 10% dropout rate. Details of the sample size calculation can be found in Appendix C.

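### Blocks of 2 or 4, stated in the protocol that sites hold, would let unmasked enrolling staff who track assignments guess about 72% of them and be certain of about 10%

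*Combined protocol and SAP*

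**What the plan says.** - Section 9.5.3 (Randomization): subjects are allocated "using a pseudo-random number generator with subjects enrolled according to a predetermined list", and the list will "use permuted blocks with random block sizes of 2 or 4". Delivery is on paper: "The investigational site will be provided a set of envelopes with randomization assignments". The section does not give the probability of each block size, say whether each site has its own list, or describe the envelopes as sealed, opaque or numbered.
- Section 7 (Study Design): "Subjects cannot be masked as it will be obvious to them which treatment they are receiving". Staff who assess endpoints are masked.
- Section 9.7 (Masked Assessor): "The Masked Assessor should not perform the randomization". Randomization and treatment therefore fall to unmasked staff.
- Section 9.4 (Informed Consent): the consent form "will be presented and explained to each prospective subject by the investigator or a trained clinical professional". Nothing requires that person to be unaware of earlier assignments.
- Section 12.7 (Sample Size): "A total of 200 subjects, 100 in the TearCare group and 100 in the Warm Compress group, will be enrolled and randomized in the study". Section 7.3 (Study Centers) allows up to 15 centers, and "No center will have more than 20% of the target enrollment".
- Sections 13 and 18.4: site initiation covers the protocol in detail and the randomization procedures, and each principal investigator signs the protocol. Sites therefore know the block sizes.

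**The concern.** Permuted blocks keep the arms balanced by making later assignments depend on earlier ones. If the person deciding whom to approach has seen the earlier assignments and knows the block sizes, part of the list is predictable. Small blocks make it more so.

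There is room to use such knowledge. Several exclusion criteria in Section 8.2 turn on the investigator's judgement or on clinical significance, and the choice of whom to approach, and when, is open. Someone who expects the next assignment to be TearCare could, even without intent, bring forward a patient thought likely to do well.

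The arms could then differ at entry. Masked assessment protects the measurement of TBUT, not the composition of the arms. The primary model in Appendix C, Section 23.1.1, adjusts for each eye's baseline TBUT, which covers selection acting through that variable only. OSDI, the key secondary endpoint, is reported by unmasked subjects and gets no protection from assessor masking.

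**Working it through.** The plan states no predictability figure, so there is none to reproduce.

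**Inputs.** Blocks of 2 or 4 and 1:1 allocation (Sections 9.5.3 and 12.7). Average site size 200/15 = 13.3 subjects; largest site 0.20 × 200 = 40 (Section 7.3).

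**Assumptions not in the documents.** The two sizes are equally likely for each block. Each site has its own sequence of whole blocks (implied by the site envelopes, not stated). The guesser knows the sizes and all earlier assignments at the site.

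**Best rule under 2/4.** Guess the arm that is behind at the site; toss a coin when the arms are level.

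**Expected correct guesses per block**
- Block of 2: 0.5 + 1 = 1.5 of 2 (75.0%).
- Block of 4: the first guess scores 0.5 and the second 2/3. With probability 1/3 the imbalance is then 2 and the last two guesses are both right (2). With probability 2/3 the arms are level and the last two score 0.5 + 1 = 1.5. Total: 0.5 + 2/3 + (1/3 × 2) + (2/3 × 1.5) = 17/6 = 2.833 of 4 (70.8%).

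**Long-run share correct.** With p the probability of a block of 2:
(1.5p + 2.833(1 − p)) / (2p + 4(1 − p)).
At p = 0.5: 2.167/3 = 72.2%. At p = 0.25: 2.5/3.5 = 71.4%. At p = 0.75: 1.833/2.5 = 73.3%.

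**Long-run share certain.** An assignment is certain only after an imbalance of 2. Only a block of 4 can produce that. It happens in 1/3 of such blocks and fixes the next two assignments:
((1 − p) × 1/3 × 2) / (2p + 4(1 − p)).
At p = 0.5: 0.333/3 = 11.1%. At p = 0.25: 14.3%. At p = 0.75: 6.7%.

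**Finite sites, p = 0.5** (exact enumeration at n = 13 and 14; simulation at n = 20 and 40)

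| Subjects at site | Guessed correctly | Known for certain |
|---|---|---|
| 13 | 70.4% | 10.0% |
| 14 | 71.7% | 10.0% |
| 20 | 71.8% | 10.4% |
| 40 | 72.0% | 10.8% |

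Ten percent of 200 is about 20 assignments.

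**Other block sets** (simulated optimal guesser, sizes equally likely within each set)

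| Sizes | Guessed, n = 14 and 40 | Certain, n = 14 and 40 |
|---|---|---|
| 2/4 | 71.7%, 72.0% | 9.9%, 10.7% |
| 4/6/8 | 66.7%, 67.7% | 2.4%, 2.4% |
| 2/4/6/8 | 67.7%, 68.4% | 1.6%, 1.8% |
| 4 only | 69.1%, 70.8% | 28.6%, 33.3% |

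Adding 6 and 8 brings certain knowledge down to about 3 to 5 assignments of 200 (1.5-2.5%), whether or not blocks of 2 stay. Removing blocks of 2 without adding larger ones roughly triples it.

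**Cost in balance.** The largest possible within-site difference is half the largest block: 2 now, 4 with blocks of 8. Suppose that all 15 sites stopped at a difference of 4, with direction left to chance. The typical overall difference would be 4 × √15 = 15.5 subjects, and efficiency relative to equal arms would be 1 − (15.5/200)² = 0.994.

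**The case against.** The best case for the plan is that these figures are a ceiling and that other features limit steering. Baseline endpoint assessments, including TBUT, slit lamp and gland scoring, are done by the Masked Assessor (Sections 9.5.1 and 9.7), so several findings that bear on eligibility come from someone who does not randomize. Baseline exams and randomization fall in the same visit. Subjects count as enrolled at consent even if they then fail eligibility (Section 9.4), and Section 12.3 promises full accounting, so exclusions after consent leave a trace. All of this stands, but the decision whom to approach comes before all of it.

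It is also fair that 72% should not be set against 50% as if block size explained the gap. The alternatives still give 67-68%, so block size accounts for roughly 4 to 5 points. Most of the rest comes from blocking within site when past assignments are visible.

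Four stronger readings are tempting, and the documents do not support them:
- A reader might infer that blocks of 2 are the fault and that dropping them is the remedy. The second table shows otherwise.
- A reader might infer that everyone at a site knows all past assignments. Section 7 implies only that each subject knows his or her own treatment, and the endpoint assessors are masked.
- A reader might infer that nothing in the analysis helps. Adjustment for baseline TBUT covers part of any selection.
- A reader might infer that envelopes are opened before eligibility is settled. The published text omits the baseline procedures (Section 9.5.2), so this cannot be judged.

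**Conclusion.** The point holds as a low-severity design improvement. With blocks of 2 or 4 disclosed to sites, a diligent tracker could guess about 72% of assignments (70-72% at sites of 13 to 40 subjects) and be certain of about 10%. The first figure barely moves with the unknown mix of block sizes (71% to 73% in the long run). The second does: 7% to 14% as the probability of a block of 2 runs from 0.75 to 0.25. Both rest on a separate sequence per site and on staff who track all earlier assignments.

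The figures describe what could be predicted. They do not show that anyone would act on it, and a reader should not infer that the trial is biased. If selection did occur on features other than baseline TBUT, neither assessor masking nor the primary model would fully correct it.

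**What to change.** 1. Remove the block sizes from Section 9.5.3. Say only that permuted blocks of random size are used, and hold the sizes and their probabilities in a restricted randomisation document.
2. Add larger random sizes, for example 4/6/8 or 2/4/6/8. Either brings best-guess success to about 67-68% and certain knowledge to about 1.5-2.5%.
3. State in Section 9.5.3 whether each site has its own sequence, and what safeguards the envelopes carry (sealed, opaque, sequentially numbered).
4. Optional: release each assignment through the EDC once eligibility is confirmed, but only if the existing system already supports it. Section 14.1 describes the EDC as data capture only, so this step is not costed here.

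Items 1 to 3 need a new list before the first subject is randomized and a few sentences of protocol text. The price is a possible within-site imbalance of 4 subjects instead of 2, with negligible effect on power. Predictability of about two in three will remain while allocation is blocked within site and past assignments are visible.

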9.5.4 TREATMENT FOR TEARCARE GROUP

Subjects randomized to the TearCare Group will undergo the following procedure. Refer to the TearCare Instructions for Use for detailed instructions for operating the TearCare System.

9.5.5 TREATMENT FOR WARM COMPRESS AND LID MASSAGE GROUP

- Subjects randomized to the Warm Compress and Lid Massage Group should be provided with the written instructions for how to perform the daily warm compress and lid massage (per the method described by Finis, et al⁴⁷) at home. These instructions are provided in Appendix B.
- 2. Go over the instructions provided in Appendix B and have the subject perform each step in the presence of study staff. This is to ensure the subject properly understands the instructions.
- Immediately following the warm compress treatment, ask the subject to assess
 whether s/he experienced any ocular discomfort or pain during or immediately
 after the treatment using the scales provided on the case report form.
- 4. Instruct the subject to perform the warm compress/lid massage once every day.
- 5. Provide the subject with a copy of the Warm Compress Use Log and instruct them to record each time they perform the warm compress/lid massage treatment.
- 6. Instruct the subject that if they require lubricant drops to relieve dry eye symptoms during the follow-up period, they should only use Refresh Plus® drops which will be supplied to them in single-use vials by the investigator. Provide the

- subject with a supply of these single-use vials. Record on the Refresh Plus Vials worksheet how much is provided to the subject.
- 7. Instruct the subject that they should not reuse the vial. Once opened, they should discard the vial. Instruct the subject to bring the unused vials back at the next follow-up visit so that they can be counted.

9.6 FOLLOW-UP VISITS

9.6.1 FOLLOW-UP VISIT ROUTINE PROCEDURES

Prior to the Visit: Reminder Call

A few days before the follow-up visit, it is recommended that the coordinator contact the subject to remind them to bring their unused Refresh Plus vials and, if they are in the warm compress group, their Warm Compress Log.

Also, since dry eye drops and lubricants can affect the endpoint assessments, it is important to remind subjects, on the day of the Follow-up visit, not to use any of these products before the Follow-up visit.

At the Beginning of the Follow-up Visit: Maintaining Masking of Study Personnel

Endpoint assessments performed during the Follow-up visit must be performed by the Masked Assessor (See Section 9.7).

At the beginning of the follow-up visit, the coordinator should remind the subject to not reveal their randomization group to the study personnel who will be performing the follow-up exams.

Order of Procedures During the Follow-Up Visit

Follow-up procedures will be performed per the Study Schedule provided in Table 3 (page 28) and the methods included in Appendix A. Since certain tests/exams can impact the ability to perform other tests/exams, the following tests and exams should be performed in this order:

- 1. Questionnaires
- 2. Manifest refraction and ETDRS Best-corrected visual acuity
- 3. Slit Lamp Exam
- 4. Tear Breakup Time
- 5. Corneal and conjunctival staining score
- 6. Meibomian Gland Secretion Scoring

CONFIDENTIAL Sight Sciences

- 7. IOP
- Assessment of adverse events

The following activities can be performed in any order:

- Medication Use
- Collection of Warm Compress Log
- · Count unused Refresh Plus Vials

At the End of the Follow-Up Visit

At the end of the follow-up visit, provide subjects with a new supply of Refresh Plus vials, if needed. Record how many vials are provided to the subject.

For subjects in the Warm Compress and Lid Massage group, provide them with a new Warm Compress Log for use in the next follow-up period.

9.6.2 6 Month Follow-up Visit: Re-Treatment

Scheduling the 6 Month Visit

Like the Baseline visit, the 6 month visit may be performed over two separate visits. If the visit is performed over two visits, then all required visit elements except the TearCare procedure and Discomfort questionnaire should be performed in the first visit. The TearCare procedure and the associated Discomfort/pain questionnaire may be performed on a separate visit, as long as it is performed within 7 days of the first visit. If the TearCare procedure is performed on a second visit, then the date of the second visit will be considered the date of the 6 Month visit for subsequent visit scheduling purposes.

At the 6 month follow-up visit, all subjects will undergo the tests and exams listed in Table 3 (page 28).

TearCare Group: Re-Treatment

After completion of the follow-up tests and exams, subjects in the TearCare group will undergo re-treatment with the TearCare System, following the instructions provided in Section 9.5.4.

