9.8 Management of Dry Eye Symptoms During Follow-Up

During follow-up, if subjects require drops to relieve their dry eye symptoms, they may use Refresh® Plus lubricant vials which have been supplied by the investigator. Other types of over-the-counter lubricants should not be used. Subjects should bring the unused vials to each follow-up visit so that they can be counted.

Subjects should not use Restasis or Xiidra during the study. Use of these drugs will result in the subject being excluded from the "Per Protocol" analysis from the time of initiation of these drugs forward.

Subject should not be treated with other dry eye treatments (e.g. LipiFlow, punctal plugs, etc.) during the course of the study. Administration of these treatments will

result in the subject being excluded from the "Per Protocol" analysis from the time of initiation of these treatments forward.

NOTE: If a subject had a punctal plug at the baseline visit and it falls out during the study, it should be replaced.

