23 APPENDIX C - STATISTICAL ANALYSIS PLAN

23.1 ENDPOINTS AND ANALYSIS METHODS

23.1.1 PRIMARY EFFECTIVENESS ENDPOINT

The primary effectiveness outcome is the change from baseline in Tear Break-Up Time (TBUT) at the 1 month follow up. TBUT will be analyzed using a linear mixed effects (LME) model. This will allow for the proper incorporation of within-person correlation into the statistical tests, and will also allow for adjustment for baseline measurements.

The linear mixed effects model for TBUT can be written as follows:

$$y_{ij} = \beta_0 + \beta_1 T_i + \beta_2 TBUT_{ij,0} + b_{0i} + \epsilon_{ij}$$

Where

- $TBUT_{ij,0}$ is the baseline TBUT value for subject i, eye j, week 0.
- y_{ij} is the 1 month change from baseline TBUT for subject i, eye j.

$$y_{ij} = TBUT_{ij,4} - TBUT_{ij,0}$$

- T_i is the 0,1 treatment indicator for subject i
- $\beta_0, \beta_1, and \beta_2$ are the fixed effect parameters
- b_{0i} is the random effect (random intercept term) for subject i

$$b_{0i} \sim N(0, \sigma_a^2)$$

ullet ϵ_{ii} is the normally-distributed error term

$$\epsilon_{ij} \sim N(0, \sigma_e^2)$$

• $\{b_{0i}\}$ and $\{\epsilon_{ij}\}$ are independent

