23.1.6 Modeling of Extended Follow-up Results

If the primary endpoint is successful at one month, then as a supplemental analysis we will fit linear mixed effects models to the 1-3- and 6-month longitudinal results.

The chosen model will allow us to evaluate the following:

- Maintenance of the Treatment effect using the full longitudinal data on each subject, providing some guide as to an appropriate retreatment schedule,
- A more detailed evaluation of the baseline effects, if any.

A summary of any model selection process, as well as more detailed output from the selected model, will be provided in the final report.

For the TearCare subjects only, the data from all visits out to 12 months will be used to further investigate the durability of the treatment effect. Similar LME modeling will allow us to evaluate their change from baseline out to 12 months. However since the Warm Compress group will crossover to TearCare at 6 months, there will be no control group to provide an unbiased comparison at the 7, 9 or 12 month points.

For the Warm Compress subjects who cross over, their combined 6 through 12-month data will be analyzed separately (again, using appropriate LME modeling) to evaluate their response to the cross over TearCare treatment. In this analysis their 6-month (precrossover) measurements will be used as the new "baseline" that will be used to compare with their 7-, 9- and 12-month outcomes. Again, there will be no control group for comparison.

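### The lubricant abstention instruction differs between the Baseline and Follow-up visits, so uncontrolled changes from baseline mix two measurement conditions

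*Combined protocol and SAP*

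**What the plan says.** For the Baseline visit, protocol section 9.5.1 tells staff to "instruct subjects not to use any of these products within 2 hours of the Baseline visit". For later visits, section 9.6.1 has them remind subjects, "on the day of the Follow-up visit, not to use any of these products before the Follow-up visit". No number of hours is given there. Both sections give the same reason; section 9.6.1 words it as "since dry eye drops and lubricants can affect the endpoint assessments".

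Three other parts of the plan bear on this:

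- **Population.** Inclusion criterion 3 (section 8.1) is "Reports having to use artificial tears or lubricants regularly". During follow-up, section 9.8 allows the supplied Refresh Plus as needed and adds: "Other types of over-the-counter lubricants should not be used".
- **Primary analysis.** SAP section 23.1.1 states: "The primary effectiveness outcome is the change from baseline in Tear Break-Up Time (TBUT) at the 1 month follow up". The model has a treatment term, where T "is the 0,1 treatment indicator for subject i", and a term for baseline TBUT.
- **Long-term analysis.** SAP section 23.1.6 will use TearCare subjects alone to "evaluate their change from baseline out to 12 months", and says that no control group is available at 7, 9 or 12 months. Warm Compress subjects who cross over are analysed from their 6-month value as a new baseline.

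No visible section reconciles the two instructions or asks for the time since the last drop. Section 9.6.1 lists only medication use and a count of unused vials.

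**The concern.** By the protocol's own reasoning, recent lubricant use is a condition of measurement. A change score is easy to interpret only if that condition is the same at both ends. Here a drop used three hours before an afternoon visit is allowed at baseline but not at follow-up.

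Elsewhere the protocol holds conditions constant. It asks for the same assessor throughout (section 9.7), the same tonometry method at each visit (section 21.9) and a fixed order of tests (section 9.6.1).

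At stake is any figure presented as improvement since baseline without a concurrent comparison. Part of it could reflect the change in abstention and not the treatment. The two uncontrolled estimates of response to TearCare would also start from different conditions. The TearCare arm starts from a value under the 2-hour instruction, and the crossover subjects start from a value under the follow-up instruction.

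**Working it through.** **Inputs.** From the documents: the two instructions (9.5.1, 9.6.1), and the planned mean TBUT changes of 6 s (SD 3) for TearCare and 4 s (SD 2) for control (SAP 23.2.1). The plan gives no figure for the effect of abstention, so there is none to reproduce. Shift sizes below are assumptions.

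**Step 1: how far the instructions differ.** Suppose a visit falls W hours after waking.

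- Baseline: free of drops for the last 2 hours.
- Follow-up: free of drops for about W hours, reading the instruction as the part of the visit day before the visit.
- The gap is about W - 2 hours when W exceeds 2, and close to nothing otherwise.

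As an illustration, for waking at 07:00 a visit at 09:00 gives W = 2 and no gap. A visit at 16:00 gives W = 9 and a gap of 9 - 2 = 7 hours. Visit times are not given.

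In 9.6.1 the words about the day of the visit may instead describe when to give the reminder. The follow-up instruction then has no stated length. On either reading it is not the 2-hour instruction.

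**Step 2: where an offset goes.** Let d be the mean effect of the difference in abstention on a change score, the same in both arms.

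- Within TearCare: observed change = true change + d.
- Within control: observed change = true change + d.
- Between arms: (6 + d) - (4 + d) = 2 s, whatever d is.
- Crossover subjects, month 6 to months 7, 9 and 12: both ends are under the follow-up instruction, so d does not enter.
- TearCare only, baseline to month 12: true change + d, with nothing to subtract it from.
- TearCare, month 1 compared with month 12: d is in both and cancels. The level relative to baseline moves, but the course over follow-up does not.

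A simulation of a baseline-adjusted comparison agrees (90 per arm, one value per subject, planned means and SDs, 1,000 runs):

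| Shift in follow-up TBUT, both arms | Within-TearCare change | Between-arm effect |
|---|---|---|
| none | 5.98 s | 1.97 s |
| -1 s | 5.00 s | 2.00 s |

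**Step 3: size of d.** Assume that a share p of subjects has baseline TBUT shifted by s seconds because of drops used 2 or more hours earlier. Then the absolute size of d is p × s.

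| p | s | p × s | Divided by 6 s |
|---|---|---|---|
| 0.25-0.50 | 0 s | 0 s | 0% |
| 0.25 | 0.5 s | 0.125 s | 2% |
| 0.50 | 1 s | 0.5 s | 8% |

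The range must include zero, because the documents do not say that a drop used more than 2 hours earlier still affects TBUT. They give no direction either. If residual drops lengthened TBUT at baseline, improvement would be understated.

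**The case against.** The strongest answer is that the trial's conclusions rest on randomised comparisons, and these are not shown to be affected. That stands. Section 9.5.1 places the baseline exams ahead of randomisation in the first visit, so abstention at baseline cannot depend on the arm. The follow-up instruction applies to both arms.

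A reader might still infer bias in the primary test, since arms may come to differ in lubricant use. A differential shift would indeed matter: assumed shifts of -1 s in TearCare and -0.5 s in control move the between-arm effect from 2 s to about 1.5 s. But nothing in the documents shows such a difference.

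Other stronger readings also fail:

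- **A full day of abstention before follow-up.** The text covers at most the visit day up to the visit, not the preceding 24 hours.
- **Most subjects are affected.** Criterion 3 says that use is regular. It does not say that drops were used on the day of the baseline visit and more than 2 hours before it.
- **All durability results are affected.** Step 2 shows that the randomised tests at 3 and 6 months, the crossover analysis and the course from month 1 to month 12 are not.
- **Eligibility and power suffer.** The TBUT threshold is not visible, and any effect on eligibility would come from the 2-hour instruction alone, not from the mismatch. Noise in the baseline covariate costs only precision. Planned TBUT power recomputes to above 99.9% with 90 subjects per arm, even with a design effect of 2 (assumed, with two-sided alpha of 0.05).

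It is also fair to say that the SAP already admits the lack of an unbiased comparison after month 6, and that section 6.1 lists those time points as exploratory. This lowers the stakes but does not explain why the instructions differ. Finally, section 9.5.2, Table 3 and the case report forms are not in the public text. A field for last drop use may exist there, though it would not remove the conflict between 9.5.1 and 9.6.1.

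**Conclusion.** The mismatch is real, and its consequence is narrow. Sections 9.5.1 and 9.6.1 give one reason and two different instructions, and no visible section reconciles them. What is exposed is the within-arm mean change from baseline and the TearCare-only change from baseline out to 12 months. Under the assumed shift of 0 to 1 s in 25-50% of subjects, these would be off by 0 to 0.5 s, or 0-8% of the planned 6 s. The size rests wholly on that assumption, and it shrinks towards zero for early-morning visits.

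The primary test, the randomised comparisons at 3 and 6 months, the crossover analysis and the sample size need no change on this account. This is a cheap improvement and not a flaw that threatens the trial's main result.

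**What to change.** Reconcile sections 9.5.1 and 9.6.1 so that one identical abstention instruction applies at the Baseline visit and at every follow-up visit with endpoint assessments. Which instruction to use is for the sponsor to decide. Word it so that its length is plain and cannot be confused with the timing of the reminder. Record the time of the last drop at each visit, if the case report form does not already do so, so that departures can be described.

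The cost is one sentence of protocol wording and possibly one form field.
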